Using a randomized experimental design, 300 parents of 2-5 year old children (predominantly African American and economically disadvantaged) referred for behavior problems to the Family Center at Kennedy-Krieger Institute will be randomized to Parent-Child Interaction Therapy (PCIT; n=150) or Chicago Parent Program (CPP; n=150). Data on child behavior problems, parent discipline strategies, parenting self-efficacy, observed parent behavior, parent stress, and depression will be obtained from all participants at baseline and post-intervention assessments. Social risk will be assessed at intake. Parent satisfaction, attendance, and engagement in the intervention will be obtained at post-intervention. Clinical costs related to PT and non-PT treatment will be measured monthly. This innovative study will be the first to compare the effectiveness, cost, and social validity of a brief treatment designed with and for ethnic minority parents of young children against a well-established treatment considered to be the "gold standard." Determining whether a PT treatment can yield comparable effects for low-income, racial/ethnic minority parents of young children but at less cost, in less time, and with greater social validity is of significant public health importance.

2. Objectives: To compare the:

1. Effectiveness of PCIT and CPP for reducing behavior problems in a predominantly African American sample of children 2-5 years old from low-income communities. It is hypothesized that CPP will be equally as effective as PCIT for reducing child behavior problems based on parent report and observation.
2. Effectiveness of PCIT and CPP for improving parenting behavior and self-efficacy among a predominantly African American sample of parents of 2-5 year old children from low-income communities. It is hypothesized that CPP will be equally as effective as PCIT for improving parent discipline, self-efficacy, and observed parenting behavior.
3. Perceived social validity of PCIT and CPP based on parent satisfaction scores, treatment attendance, and parent engagement ratings (i.e., active parent participation in the intervention

Date: January 30, 2012
Principal Investigator: [name]
Application Number: NA_00039328

sessions). It is hypothesized that parents in the CPP condition will (a) attend a higher percent of PT sessions, (b) be more engaged, and (c) report higher satisfaction than parents in PCIT.

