b. Study duration and visits: Following consent, parents will be assigned to the appropriate block consisting of the next CPP group or the next available PCIT therapist. Participating parents and children will complete three assessment phases: baseline, 4 months post-baseline, and 9 months post-baseline. Each assessment phase includes parent-report surveys on child behavior problems, parenting self-efficacy, parent discipline strategies, stress, depressive symptoms, and attachment, and a 15- minute videotaped parent-child free play interaction (Dyadic Parent-Child Interaction Coding Systems; DPICS), followed by a clean-up session. Videotaped DPICS assessments will be coded by research colleagues at the University of Iowa ([name].) A Data Use Agreement will be obtained between Drs. [name], University of Iowa and [name], Johns Hopkins School of Nursing. Assessments typically require 45-75 minutes at each phase. All measures are described in Table 1 below.

Table 1. Parent-Child Variables, Measures, Informant, Items, Assessment Time-points*, Reliability, Validity

Variables	Measure(s)	Informant	# of Items	When Assessed	Reliability	Validity Evidence
Child Behavior Problems (parent)	Child Behavior Checklist (CBCL/1½-5) (Externalizing Scale & Internalizing Scale)	Parent	99	T1, T2, T3	.86-.89	[40; 41]
Child Behavior Problems (observed)	Dyadic Parent-Child Interaction Coding System (DPICS) (non-compliance, destructives, physical negatives, smart talk, cry, whine, yell)	Observer	7	T1, T2, T3	.73	[22; 57; 58]
Parent Self-Efficacy	Toddler Care Questionnaire (TCQ)	Parent	38	T1, T2, T3	>.93	[22; 57; 59; 60]
Parent Discipline	Parenting Questionnaire (PQ) (Warmth, Following Through, Corporal Punishment subscales)	Parent	50	T1, T2, T3	.68-.84	[22; 61]
Parent Depression	Center for Epidemiologic Studies Depression Scale-Revised	Parent	20	T1, T2, T3	>.85	
Parent Attachment	Attachment Style Questionnaire	Parent	40	T1	Test-retest .75-.80	
Parent Behavior	DPICS (Praise, Commands, Physical Coerciveness, Critical Statements, Positive/ Negative Affect)	Observer	10	T1, T2, T3	.88-.90	[22; 57; 58]
Social Validity: parent satisfaction w/ PT	Parent Satisfaction at end of program	Parent	4-12	T2 -CPP T3-PCIT	NA (items analyzed separately)	[34; 55; 57]
Social Validity: Degree to which parent actively participated in PT	Parent Engagement Scale	Clinician	7	T2-CPP T3-PCIT	.87	[35]

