Exclusion criteria are parent(s) who (a) has (have) severe mental illness that would interfere with their ability to participate in PT (measured by the Psychosis Subscale of the Basic-24 or diagnostic intake clinician assessment) and/or (b) is (are) actively using drugs or alcohol, based on clinician assessment at intake. Foster parents or relatives without legal status for the child are excluded since they may not be able to complete the study.. Children who are actively suicidal, psychotic, or who have significant developmental delay (i.e., fail developmental screening using Ages and Stages Questionnaire at intake), congenital, genetic, or sensory abnormalities that interfere with the child’s understanding, cooperation, and/or participation in PCIT or CPP will be excluded and referred for appropriate treatment services or hospitalization. Children diagnosed with autism or Pervasive Developmental Disorder will also be excluded since there is no evidence that CPP or PCIT is effective with these populations.

6. Drugs/ Substances/ Devices

- a. NA
- b. NA.
- c. NA

7. Study Statistics

- a. Primary outcome variables: Child behavior problems (parent report and observed from video recorded parent-child play/clean-up), parenting self-efficacy, parent discipline, parent behavior (observed from video recorded play/clean-up), parent satisfaction, parent engagement in the intervention, parent attendance in PT sessions.
- b. Secondary outcome variables: cost variables are those related to (1) time required to administer PT (including lost time for missed appointments) and additional non-PT therapy services used by parent or child (i.e., individual therapy, medications); (2) therapist time, (3) parent time, (4) childcare provided during CPP sessions; (5) space (including one-way mirror).
- c. Sample Size and Statistical Plan: Sample size in this equivalence study is designed to determine whether CPP is as effective as PCIT for the targeted clinical population (i.e., outcomes do not differ clinically or statistically). We used CBCL scores (child behavior problems) to estimate the sample size positing the null hypothesis that the absolute difference in the post intervention means between the CPP and PCIT groups will be > 0.5 standard deviations (i.e., > 5 point difference on the CBCL). The alternative hypothesis is that the absolute difference in the two means is less than or equal to 0.5

Date: January 30, 2012
Principal Investigator: [name]

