Application Number: NA_00039328

standard deviations. We will use the more conservative two-sided test. Thus, with 300 participants (150/condition) we will have 99% power to detect this difference using a two-sample comparison of means with alpha=0.05.

Hypothesis testing will mainly be conducted using repeated-measures MANOVA. Should the MANOVA be significant, univariate ANOVA will follow to identify the source of those differences. MANOVA was determined to be a more desirable approach than random regression models because MANOVA corrects for multiple tests of hypotheses. All baseline difference analyses and hypothesis testing will be conducted using 2-tailed tests and alpha =.05 (except tests to examine baseline differences between conditions, which will use .01 to correct for the multiple tests of hypotheses).

d. Early stoppage rules. Interventions will be discontinued if (a) more than 50% of parent participants in either condition report dissatisfaction on consumer satisfaction surveys with their assigned intervention or (b) more than 50% of child participants' CBCL scores (in either condition) worsen from baseline by $> .5$ SD. In this event, the research team will immediately convene with the members of the DSM committee to carefully review the protocol, reasons for dissatisfaction, and recommendations for change. A data safety and monitoring committee will meet early in the first year of the study to make additional recommendations for stoppage rules.

8. Risks

- a. Medical risks. Parent-Child Interaction Therapy and the Chicago Parent Program are psychosocial parent training interventions that have shown no evidence of medical risk. The major risks of this study are disclosure of confidential information and discomfort with the personal nature of some of the survey questions. These risks are no greater than what parents would be exposed to in a mental health treatment setting.
- b. Efforts to minimize risk. Efforts have been taken to minimize risk through appropriate training of research and clinical staff and the use of random number subject identifiers. All therapists have licensed and experienced therapists and have completed the appropriate training (PCIT or CPP).

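### Hypothesis 3(c), higher satisfaction with CPP, rests on 4 to 12 separately analysed items, with no stated decision rule or error control that fits them

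*Combined protocol and SAP*

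**What the plan says.** - **Hypothesis.** Section 2, Objective 3 compares social validity "based on parent satisfaction scores, treatment attendance, and parent engagement ratings". Part (c) of its hypothesis is that CPP parents will "report higher satisfaction than parents in PCIT".
- **Status.** Section 7a ends its list of primary outcome variables with "parent satisfaction, parent engagement in the intervention, parent attendance in PT sessions".
- **Measure.** Section 4b, Table 1 lists a parent-completed satisfaction measure of 4-12 items, taken at T2 (4 months) in CPP and T3 (9 months) in PCIT. Its Reliability column reads "NA (items analyzed separately". The range of items is not explained.
- **Level.** Section 7c: "All baseline difference analyses and hypothesis testing will be conducted using 2-tailed tests and alpha =.05". The only exception is for baseline comparisons, which use .01 because there are many of them.
- **Method.** Section 7c: "Hypothesis testing will mainly be conducted using repeated-measures MANOVA", and then "Should the MANOVA be significant, univariate ANOVA will follow to identify the source of those differences". MANOVA is preferred over random regression models on the ground that "MANOVA corrects for multiple tests of hypotheses".

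**The concern.** One primary hypothesis has between 4 and 12 candidate tests, and the plan does not say how they combine into an answer. No total score, lead item or minimum number of items favouring CPP is named, and no adjustment across items is given.

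The plan is alert to multiplicity. It chose MANOVA for that reason and tightened the level for baseline comparisons. But the correction it names is a repeated-measures model, and satisfaction has no baseline and no repeated measurement.

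At stake is the claim that parents prefer CPP, which could rest on one item among several. Objective 4 carries the same expectation into the cost-consequence comparison, so a chance finding would spread to that conclusion too.

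**Working it through.** **The plan's own figure.** The only calculated design figure is 99% power for the CBCL comparison: 150 per arm, 5 points = 0.5 SD (so SD 10), two-sided .05. The standard error is 10 × √(2/150) = 1.155, and 5/1.155 = 4.33. Power is Φ(4.33 − 1.96) = 99.1%, so the figure reproduces. It concerns the CBCL and has no bearing on satisfaction, for which no error rate is stated.

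**Does the named model fit?** A repeated-measures MANOVA needs the same variables measured on more than one occasion. Table 1 gives satisfaction one occasion per arm, and not the same one. As written, the model does not apply.

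**Inputs for the error rate**
- Number of items k: 4 to 12 (Table 1). How many are common to both arms is not given.
- Level per item: two-sided .05, so .025 in the direction favouring CPP (Section 7c).
- Inter-item correlation: not given. Assumed 0 and 0.5, with 0.3 to 0.9 also shown.
- Decision rule: not given. Assumed that any one significant item favouring CPP counts as support, with no gate.

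**Independent items, no true difference**
- Favouring CPP: 1 − 0.975^4 = 9.6%; 1 − 0.975^12 = 26.2%.
- Either direction: 1 − 0.95^4 = 18.5%; 1 − 0.95^12 = 46.0%.

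**Correlated items** (equicorrelated normal test statistics, 400,000 draws)

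| Correlation | Favouring CPP, 4 items | Favouring CPP, 12 items | Either direction, 4 items | Either direction, 12 items |
|---|---|---|---|---|
| 0.3 | 8.8% | 20.2% | 17.4% | 39.7% |
| 0.5 | 7.8% | 16.1% | 15.7% | 31.9% |
| 0.7 | 6.5% | 11.7% | 12.9% | 23.2% |
| 0.9 | 4.7% | 6.7% | 9.4% | 13.4% |

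The benchmark for a false result favouring CPP from one two-sided .05 test is 2.5%.

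**If a between-group MANOVA gate at .05 were added.** With no item truly different, a false item-level finding in either direction would occur at most 5% of the time. That protection lapses once one item truly differs and the gate is passed. For 12 independent items, the other 11 at .05 give 1 − 0.95^11 = 43.1% in either direction, or 1 − 0.975^11 = 24.3% favouring CPP.

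**With Holm.** The smallest p-value is compared with .05/k: .0125 for 4 items and .0042 for 12. With independent items and no true difference, the chance of any false finding is 4.9% in both cases. Favouring CPP it is 1 − (1 − .00625)^4 = 2.5% and 1 − (1 − .00208)^12 = 2.5%.

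**The case against.** The strongest reply is that the Table 1 entry stands in the Reliability column. It explains why no coefficient is given and shows that the items are not summed. It does not say that each item is an unadjusted confirmatory test, or that one significant item settles the hypothesis. Unsummed items could be the joint outcomes of an ordinary between-group MANOVA, with item-level ANOVAs following, and Section 7c says only that testing will mainly take the repeated-measures form. This stands in part: whether a gate covers these items is unclear, not settled. But the plan does not state one, and such a gate would protect the item-level claims only while no item truly differs.

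A reader might also infer a 46% chance of a false satisfaction claim. The documents do not support that. The figure needs 12 items comparable across arms, independence, no gate, an any-one-item rule and errors counted in either direction. Hypothesis 3(c) concerns CPP being higher, for which the most is 26%. Items from one survey answered by the same parent are likely to be positively correlated, which lowers it further. If the range of 4 to 12 reflects forms of different length in the two arms, as few as 4 items might be comparable.

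Finally, a mean score presumes shared items on compatible scales, and Table 1 reports no reliability for one. That stands, and it is why a composite is offered below only as an option.

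**Conclusion.** The concern holds as a gap in error control on a listed primary outcome. Following the text, the satisfaction items are analysed separately at two-tailed .05. The named multiplicity correction does not fit them, and nothing else is put in its place.

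If the items are ungated and any one significant item is taken as support, the chance of a false finding favouring CPP is about 10% to 26% for independent items and 8% to 16% at an assumed correlation of 0.5. That is roughly three to ten times the 2.5% of a single test. These figures depend on the unstated correlation, the unstated number of shared items and a decision rule that the plan does not give. They show what the present wording permits, not what the investigators necessarily intend.

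**What to change.** Add to Section 7c that error for hypothesis 3(c) is controlled at two-sided .05. The default is Holm adjustment across the satisfaction items common to both arms. If those items share a scale, one prespecified test of their mean is an alternative. Choose between the two before comparative data are seen, list the common items, and report all other item results descriptively. Listing them would also settle how many of the 4 to 12 items can be compared.

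This is a cheap improvement that needs only SAP wording: no new data, visits or participants. The cost is that unadjusted single-item differences lose confirmatory status, and under Holm the first item must meet a stricter threshold.

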- a. Design: This equivalence study will use an experimental design with randomization of parents seeking behavioral treatment for their 2-5 year old children at the Family Center (FC) in [name]. Equivalence studies are used to determine whether a novel treatment or health delivery model, that might be less costly or more acceptable to the treatment population, is at least as effective as another more well-established treatment. It is important to note that the participants in this study, who experience multiple adversities associated with urban poverty and mental health problems, may require more therapeutic services than just PT. As a result, parents and children may receive additional treatment (e.g., individual therapy, medication) other than PT. However, PT treatment (PCIT or CPP) will be randomly assigned and all additional therapies provided to the participating parent or child at the Family Center or other agencies during the course of this study (type, amount, and cost) will be accounted for in the study and included as co-variates in the analyses. In addition, the effect of parent depression and stress on PT outcomes will be evaluated. The strengths of this design include (a) the ability to determine whether families exposed to one PT program need more additional treatment than families exposed to the other PT program, (b) the ability to estimate the costs of additional therapy, (c)

Date: _ January 30, 2012 _____
 Principal Investigator: _ [name] _____
 Application Number: _ NA_00039328 _____

greater buy-in from clinicians who may be concerned that randomization will negatively affect treatment outcomes for their families, and (d) enhanced external validity of the study.

This study will use a block randomization procedure to facilitate the initiation of parent groups without lengthy waiting periods. Each block will consist of the next 19 eligible parents (estimated recruitment time=3-4 months). Following intake assessment by a FC clinician to determine study eligibility, parents who meet the inclusion criteria will be invited to participate in the study. Parents who state interest in participating and agree to have their name given to the Project Director will meet individually with the Project Director (to be hired) who will describe the study and obtain informed consent. Documentation of parent's agreement to be contacted by the Project Director will be placed in the child's medical record.

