Social Validity: % of recommended PT sessions parent attends	% of 12 CPP sessions attended; % of clinician-recommended PCIT sessions attended	Clinician	1	After each PT session	NA	
Clinician Satisfaction	Perceived satisfaction with performance, PT match with parent needs, flexibility of PT model	Clinician	3	After each PT session	NA (items analyzed separately)	New measure

Date: _ January 30, 2012 _____
 Principal Investigator: _ [name] _____
 Application Number: _ NA_00039328 _____

						created for this study
**Assessment of parent psychosis/thought disorder	Clinician assessment and/or psychosis subscale from B-24	Clinician	5	Intake assessment	0.77	
Parent Stress	Parenting Stress Index-Short Form (PSI) (parent distress, parent-child dysfunction, child difficulty)	Parent	36	T1, T2, T3	.80-.91	[64; 65]
**Family Social Risk	Summed composite of poverty, < HS education, single parent, depressed, > 4 people in the home, teen parent, unemployed, parent substance abuse hx	Parent with clinician	8 yes/no items	Intake	.81	[66]
**Medical, psychosocial, and mental health history and diagnoses	Diagnostic Interview and Psychosocial History	Clinician		Intake		
**Significant developmental delay+	Ages & Stages Questionnaire, 3 rd ed.	Parent with clinician		Intake	.94	[50]

* T1=baseline, T2=4 months post-baseline, T3=9 months post-baseline; + used to establish eligibility

** Standard clinical practice assessments.

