Parents randomized to PCIT will be scheduled for weekly individual sessions with the target child led by trained PCIT therapists. Each treatment session is 1 hour. Parents randomized to CPP will be randomized to a weekly parent group led by trained CPP therapists. Each CPP session is 2 hours, scheduled on week-day evenings. Target children do not participate in CPP groups; therefore, childcare will be provided at no charge to facilitate parent attendance. Though PCIT and CPP each prescribe approximately 24 hours of treatment exposure, PCIT occurs over a longer period of time (usually 6-8 months versus CPP which occurs over 3 months). This is because (1) PCIT sessions are 1 hour shorter, and (2) PCIT treatments are delayed when parents cancel or do not show up for appointments whereas CPP group sessions continue even if some parents do not attend. All CPP sessions will be audio recorded and a random selection of CPP sessions will be reviewed for fidelity by [name] at Rush University. A random number of PCIT sessions will be videotaped and reviewed for fidelity by a research colleague certified in PCIT who works at the University of Maryland, [name]. A data use agreement will be obtained between [name] and [name] and [name].

- c. Blinding: parents and therapists cannot be blinded to treatment condition. Research assistants trained to code video recorded parent-child free play and clean-up sessions will be blind to treatment condition and hypotheses.
- d. Participants will have full access to routine care at the Family Center. If a PCIT therapist determines at the beginning of the session that the parent is in crisis (e.g., reports severe depression, domestic violence), or the parent requests using the session to discuss a non-child related crisis, they may decide to use that session for crisis intervention. This session will be documented as a non-PT session and accounted for in the analysis of total PT and non-PT treatment exposure. If the CPP therapist determines that a parent in the parent group is in crisis, or a parent requests to discuss a non-child related crisis, that therapist will meet with the parent after the CPP group to discuss scheduling a separate session.
- e. There is no control or placebo group. Participants in both conditions receive an evidence-based parenting program delivered by trained therapists.

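### Equivalence is defined by a 0.5 SD margin, but the planned MANOVA never tests that margin and no visit is named; T2 usually falls mid-PCIT

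*Combined protocol and SAP*

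**What the plan says.** **Hypothesis.** Section 7c sets the null for the sample size as "the absolute difference in the post intervention means between the CPP and PCIT groups will be > 0.5 standard deviations", equated with more than 5 CBCL points. It claims 99% power with 150 per condition and alpha 0.05. The Abstract says the outcome data "will be obtained from all participants at baseline and post-intervention assessments". Neither place ties the post-intervention label to a visit.

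**Test.** Section 7c then states: "Hypothesis testing will mainly be conducted using repeated-measures MANOVA". Univariate ANOVA follows if the MANOVA is significant. No visits, contrast, margin or confidence interval are given for this analysis.

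**Visits.** Section 4b: "Participating parents and children will complete three assessment phases: baseline, 4 months post-baseline, and 9 months post-baseline". The Table 1 footnote agrees: "T1=baseline, T2=4 months post-baseline, T3=9 months post-baseline". CBCL, the observed behavior codes, self-efficacy and discipline are all taken at T1, T2 and T3 in both arms.

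**Program length.** Section 4b, after Table 1: "PCIT occurs over a longer period of time (usually 6-8 months versus CPP which occurs over 3 months".

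**Program end.** For satisfaction and engagement only, Table 1 uses T2 in the CPP arm and T3 in the PCIT arm. It gives no such rule for the effectiveness outcomes of objectives 1 and 2.

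**Start of treatment.** Section 4a: "Each block will consist of the next 19 eligible parents (estimated recruitment time=3-4 months". Section 4b assigns families to "the next CPP group or the next available PCIT therapist". The interval from baseline to first session is not stated.

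**The concern.** Two gaps meet in the trial's central conclusion.

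First, the stated analysis does not answer the stated question. A non-significant MANOVA is not evidence that the difference is below 0.5 SD, and a significant one is not evidence that it is above. The margin plays no part after the sample size has been set.

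Second, the hypothesis could be read as referring to T2, to T3, to some combination, or to a different visit in each arm. On the protocol's own durations, with treatment starting near baseline, CPP is finished at T2 and PCIT usually is not. If T2 enters the decision, a difference in delivery speed can look like a difference between programs that end equal, or can hide a real CPP deficit because the comparator is unfinished. Leaving the visit open also allows it to be chosen after the data are seen.

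**Working it through.** **1. The plan's own figure.** Inputs from section 7c: 150 per arm, 0.5 SD = 5 points (so SD = 10), two-sided alpha 0.05. In SD units SE = √(2/150) = 0.1155, and 0.5/0.1155 = 4.33. Power = Φ(4.33 − 1.96) = 0.991, which reproduces the stated 99%. This is the formula for detecting a difference. For showing equivalence at true difference δ, power = Φ((0.5 − δ)/SE − z) + Φ((0.5 + δ)/SE − z) − 1. At δ = 0 this is 99.3% with z = 1.645 (90% interval) and 98.2% with z = 1.96 (95% interval). The sample size is therefore adequate for either reading.

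**2. Difference test against margin.** Simplify to a two-sample comparison at one visit.

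- Non-significant if the observed difference is below 1.96 × 0.1155 = 0.226 SD.
- 90% interval inside ±0.5 SD if it is below 0.5 − 1.645 × 0.1155 = 0.310 SD (3.1 points); for a 95% interval, 0.5 − 1.96 × 0.1155 = 0.274 SD (2.7 points).
- An observed difference of 0.226 to 0.310 SD is thus significant and yet equivalent by the 90% interval.
- True gap 0.2 SD: 0.2/0.1155 = 1.732, and P(non-significant) = Φ(1.96 − 1.732) − Φ(−1.96 − 1.732) = 59%.
- True gap 0.5 SD: non-significant 0.9% of the time with 150 per arm but 29% with 50 per arm. A rule based on non-significance rewards a smaller trial.

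**3. Where the visits fall** (treatment starting at baseline):

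| | CPP (3 months) | PCIT (usually 6-8 months) |
|---|---|---|
| T2, 4 months | over for 4 − 3 = 1 month | 4/8 to 4/6 = 50-67% elapsed |
| T3, 9 months | over for 9 − 3 = 6 months | over for 9 − 8 = 1 to 9 − 6 = 3 months |

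T3 follows the usual end of PCIT only if PCIT starts within about 1-3 months of baseline.

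**4. Illustrative T2 gap.** Assumptions: PCIT gain 0.61 SD (section 3, parent report, against waiting list), linear accrual, both programs equal at the end, immediate start. Gap = 0.61 × (CPP share − PCIT share).

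- 8-month course: 0.61 × (1 − 0.50) = 0.31.
- 6-month course: 0.61 × (1 − 0.67) = 0.20.
- 24 weekly hours (section 4b), none missed: 17.3/24 = 72% elapsed, gap 0.17.
- 20 weekly sessions (upper end in section 3), none missed: 17.3/20 = 87% elapsed, gap 0.08.
- CPP families wait 2 months, PCIT families do not: CPP share (4 − 2)/3 = 67%, gap 0.10 (8-month course) or 0.00 (6-month course). Wait of 3 months: share 33%, gap −0.10 or −0.20.
- PCIT gain already complete by T2: no gap.

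**5. Equivalence at T3, 150 per arm.** True difference 0: 99.3% (90% interval) or 98.2% (95%). Difference 0.1 SD: 96.5% or 93.3%. Difference 0.2 SD: 83.0% or 73.8%. With 120 per arm (20% loss, assumed) and no difference: 97.4% or 94.4%.

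**The case against.** **Non-significance may be enough at this sample size.** In step 2, 0.226 is below 0.310, so with complete data on one outcome at one visit a non-significant result does put the interval inside the margin. That stands, but it is a by-product of the numbers. It needs 1.96 SE < 0.5 − 1.645 SE, so SE < 0.5/3.605 = 0.1387, or at least 2/0.1387² ≈ 104 per arm. For a 95% interval, SE < 0.5/3.92 = 0.1276, or about 123 per arm. Section 3 cites 36% drop-out from PCIT; that loss in both arms (assumed) would leave 96. Nor does it carry over to a MANOVA with unstated visits and contrasts.

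**Table 1 already maps program end.** It does, arm by arm, but only for satisfaction and engagement. It shows the timing problem was recognised, and it adds another reading for CBCL (CPP at T2, PCIT at T3) without adopting it.

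**T3 is not neutral.** It replaces an unfinished PCIT with unequal time since program end. Fixed time from baseline and fixed time from program end are both legitimate questions. This stands: a reader might infer that T3 is the only valid visit, but the documents support only that it is the one common visit after the usual end of both programs, subject to the start-time proviso.

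**The T2 modelling is weak.** This also stands. A reader might infer that the trial has poor operating characteristics; putting gaps of 0.20-0.31 SD into the formula of step 1 gives equivalence at T2 in only 82-52% of trials whose programs end equal. The plan contains no T2-only rule. The 0.61 SD is a completers' effect against waiting list, and linear accrual has no source: section 3 describes mastery-paced phases, and section 4b attributes the longer course partly to missed sessions. A case in which CPP ends a full 0.5 SD worse needs a CPP gain of only 0.61 − 0.50 = 0.11 SD, below the 0.24-0.64 that section 3 reports from a community sample.

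**Conclusion.** The point holds. Followed as written, the plan would not test its own equivalence hypothesis, because no stated analysis uses the 0.5 SD margin; this is true at every visit and needs no modelling. The visit is also undefined for objectives 1 and 2, and on the protocol's own durations T2 usually falls mid-PCIT.

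The possible distortion at T2, about 0.08-0.31 SD, is an illustration of mechanism. It rests on the 0.61 SD gain, linear accrual and immediate start; it can shrink, reverse or vanish, and it is not an estimate of this trial's error. A reader might also infer that the 99% power claim is wrong. It is not: it reproduces, and it survives the move to an interval-based decision.

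This should be fixed before analysis. The planned data collection can support the conclusion; the decision rule is what is missing.

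**What to change.** In section 7c:

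- Decide equivalence for objectives 1 and 2 from the between-arm difference adjusted for the T1 value, with a confidence interval of stated level (90% for two one-sided tests at 0.05, or 95%) lying within ±0.5 SD, which is ±5 points on the CBCL. Do not base it on the MANOVA result.
- Name one common visit in advance and justify it. T3 is the natural candidate; word the result as a comparison at 9 months post-baseline.
- Report T2 as secondary, labelled as usually mid-PCIT.
- Report by arm the time from baseline to first session and from program end to T3, so that the start-time proviso can be checked.

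**Cost.** A change of wording and two dates per family. T3 is already collected in both arms and the sample size is unchanged. The real downside is unequal follow-up after program end (about 6 months for CPP, 1-3 for PCIT). If CPP had lost 0.2 SD by T3, equivalence would be shown in 83% of trials with a 90% interval.
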